# 5.1 Sample size reassessment

A blinded sample size reassessment (SSR) has been performed according to the protocol section 15.2.1. For each subject, the data cut-off-point for the SSR was the visit (including TCs) closest to but not before the 1st of February 2020.

Type of document	Date:	11-Aug-2022	
Document ID	Version:	4.0	
INTERNAL USE	Status: Page:	Final 44 of 79	

The conclusion of the SSR was that the reassessed sample size is 900 subjects, corresponding to a power of 81%. However, it was decided not to recruit for a new cohort as it was assessed that the SSR may not be accurate as the exacerbation rate was uncertain due to a very limited number of observations and due to the fact that the Covid-19 situation with rules of social distancing was likely to reduce transmission of respiratory infections, and thus also the number of exacerbations.

It was decided to perform a new SSR based on data sets from Cohort 1-3, however the SSR was not performed. Details are provided in section **4.8**.

# 6 DEMOGRAPHICS AND BASELINE CHARACTERISTICS

Summaries of numerical variables will display the descriptive statistics mean, SD, median, minimum and maximum and relevant quantiles.

Summaries of categorical variables will be frequency tables displaying numbers and percentages.

# 6.1 Subject disposition

A table of subject disposition displaying number and percentage of subjects screened, enrolled, included in the safety analysis set, discontinued and the primary reason for discontinuation by treatment group will be presented.

Table(s) of subject disposition by treatment group displaying number and percentage of subjects screened, randomised, included in FAS, with observation of the primary endpoint (at least 1 observation in period 4), included in PP, included in SAF, discontinued treatment, withdrawn from trial, by primary reason for discontinuation of treatment or withdrawal from trial and who completed the trial will be presented.

The overall treatment discontinuation and treatment discontinuation due to AEs will be displayed by a Kaplan-Meier plot.

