5.1 Discontinuation from IMP treatment

Subjects must be discontinued from IMP treatment and should continue in the trial for safety assessments only under the following circumstances:

- If the subject experiences 2 severe asthma exacerbations within a 12 consecutive months period
- If the subject is hospitalised due to asthma requiring treatment with systemic corticosteroids
- The subject experiences severe or persistent symptoms of oesophagitis
- If the subject becomes pregnant
- If, in the investigator's opinion, continuation with IMP treatment would be detrimental to the subject's well-being

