5.2 Discontinuation from trial

The subject and/or subjects parent/caregiver will be advised in the informed consent form that he/she has the right to withdraw from the trial at any time without prejudice. Where discontinuation from the trial is initiated by the subject, the investigator is to ascertain the primary reason for discontinuation from the list below:

- An AE for which the investigator did not consider discontinuation from the trial necessary
- Perceived insufficient therapeutic effect
- Co-existing disease
- Withdrawal of consent
- Other reasons

Additionally, the subject may at any time be discontinued from the trial at the discretion of the investigator or ALK.

Subjects must be discontinued from the trial under the following circumstances:

- If, in the investigator's opinion, continuation in the trial would be detrimental to the subject's well-being
- If subject is lost to follow-up
- If informed consent is withdrawn

If found required by ALK after discussion with the investigator, subjects may be discontinued from the trial under the following circumstances:

- If subject is treated with prohibited medication as defined in Table 2
- In case of protocol deviation, violation of eligibility criteria or deviation from the treatment plan specified in the protocol (e.g. incorrect administration of the IMP)
- If IMP is discontinued for several months

In case a subject discontinues from the trial, the discontinuation page in the eCRF should be completed. On the discontinuation page the investigator should record the date of the discontinuation, the person initiating the discontinuation and the primary reason for discontinuation. If an AE is involved in a discontinuation, this must be recorded as the primary reason. In all cases, the primary reason for discontinuation must be recorded in the eCRF and in the subject's medical records. Follow-up on the subject is necessary to establish whether the reason was an AE. If so, this must be reported in accordance with the appropriate procedures.

To the extent possible, all examinations scheduled for the final visit must be performed on subjects who receive IMP but did not complete the trial according to the protocol. If possible, the TC follow-up (TC21) should be performed and the corresponding eCRF pages should be filled in.

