If assuming a drop-out rate of 30%, a power of at least 90% and an efficacy assessment period of 20 month (86 weeks), a sample size of approximately 300 (\sim 205/0.7=293) subjects per arm should be sufficient to detect a difference in exacerbation rates of 20% when no overdispersion is present as shown in Table 13. In case of overdispersion defined by a dispersion parameter of k=0.7, a sample size of 300 (>202/0.7=288) subjects per arm would be sufficient to detect a difference in the exacerbation rates of 30%.

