15.4 Subject disposition

A table of subject disposition by treatment group displaying number and percentage of subjects screened, randomised, included in FAS, with observation of the primary endpoint, included in PP, included in safety set, discontinued IMP, discontinued trial, by primary reason for IMP and trial discontinuation and who completed the trial will be presented.

The overall IMP discontinuation will be displayed by a Kaplan-meier plot. Cumulative incidence plot will be used to show cause specific IMP discontinuation distribution.

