  - The average rhinoconjunctivitis DMS during the 2-week assessment period before V5, V6, V7, V8, V9, V10 and V11
  - The average rhinoconjunctivitis VAS during the 2-week assessment period before V5, V6, V7, V8, V9, V10 and V11
- Immunology
  - Changes from baseline in IgE, IgE-BF and IgG4 against *D. pteronyssinus* and *D. farinae* measured at V7 and V11
- Safety and tolerability endpoints
  - Treatment-emergent AEs (TEAEs), IMP-related AEs, treatment-emergent SAEs, TEAEs leading to (IMP) discontinuation, time to discontinuation due to TEAEs, solicited AEs
  - Vital signs, FEV1, clinical laboratory values and physical examination during treatment and at the final visit (V11)

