TEAEs leading to IMP interruptions, serious TEAEs (SAEs) and TEAEs leading to IMP discontinuations will be summarised by SOC, PT and treatment group in separate tables. A cumulative incidence plot will be used to show the cause specific distribution of IMP discontinuation due to TEAEs.

Most frequent TEAEs are those AEs (defined as MedDRA PTs) that are present in at least 2% of subjects with active treatment. Most frequent TEAEs and most frequent IMP-related AEs will be summarised by SOC, PT and treatment group in separate tables.

Additionally, the following TEAEs will be summarised by treatment group displaying the number and frequency of subjects having the event as well as number of events, see **0** (Appendix 3: Preferred Terms):

- asthma related events
- asthma related hospitalisations

Type of document	Date:	11-Aug-2022	
Document ID	Version:	4.0	
	Status:	Final	
INTERNAL USE	Page:	40 of 79	

Κ

- worsening of asthma requiring medication
- asthma related symptoms leading to IMP discontinuation
- solicited TEAEs
- TEAEs excluding solicited events and clinically relevant asthma exacerbations

Onset of a TEAE is defined as time (e.g. minutes or days) from first IMP intake to start of the first TEAE of a given PT. An onset of 1 day means that the TEAE has started on the day of first IMP intake.

Resolution time of a TEAE is defined as days from start of the TEAE until the TEAE is resolved, e.g., recurrent TEAEs like oral pruritus that occurs every day for 1 minute on 5 days in a row will have a resolution time of 5 days.

Resolution time and onset in minutes/hours/days will be summarised by treatment group for most frequent TEAEs and for local application site TEAEs displaying mean, SD, median, 5% percentile, 95% percentile, minimum and maximum.

For solicited TEAEs the duration in minutes on the first day of IMP intake will be summarised.

All AEs will be listed including non-TEAEs.

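### SAP 6.1 plots treatment discontinuation due to AEs by Kaplan-Meier, against the cumulative incidence specified in Protocol 15.4 and SAP 4.5.2, and so shows a curve at or somewhat above the proportion who stop for AEs

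*SAP*

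**What the plan says.** Protocol 15.4 separates two displays. For all causes together: "The overall IMP discontinuation will be displayed by a Kaplan-meier plot". For single causes: "Cumulative incidence plot will be used to show cause specific IMP discontinuation distribution".

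SAP 4.5.2 follows the protocol for the adverse-event cause: "A cumulative incidence plot will be used to show the cause specific distribution of IMP discontinuation due to TEAEs".

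SAP 6.1 does not: "The overall treatment discontinuation and treatment discontinuation due to AEs will be displayed by a Kaplan-Meier plot". It states neither a censoring rule nor an analysis set for this plot.

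SAP 1.1.7 names "time to discontinuation due to TEAEs" among the safety and tolerability endpoints, so the quantity plotted is a declared endpoint. SAP 4.8, which records changes from the protocol, does not mention the discontinuation plots.

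**The concern.** A subject who stops treatment for a reason other than an AE can no longer stop because of an AE, so the other reasons are competing events. The documents show that such reasons exist:

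- Protocol 5.2 lists withdrawal of consent and "Perceived insufficient therapeutic effect" as reasons for leaving the trial. SAP 1.1.9.3 says only 3 subjects stopped treatment without leaving the trial at the same time, so these reasons largely apply to treatment as well.
- Protocol 5.1 requires treatment to stop in case of pregnancy.
- SAP 3.1 reports that all 9 subjects at site 613 were discontinued after dual enrolment was found there. They remain in the safety set.

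A Kaplan-Meier curve for AE stops would normally treat these subjects as censored. It then estimates AE stopping in a hypothetical setting with no other reason to stop, not the share of subjects who actually stop for AEs. The SAP would therefore yield two curves, in 6.1 and 4.5.2, with different values for essentially the same risk, and it does not say which one governs.

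**Working it through.** **Figures in the plan.** The documents give no figure for AE-caused discontinuation, so none can be reproduced. The only planning figure for total loss is the 30% drop-out allowance in Protocol 15.1, where 205/0.7 = 292.9 matches the stated 293 per arm. It is used here as an assumed total discontinuation.

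**Inputs.**
- D = total treatment discontinuation = 30% (assumption).
- s = share of stops due to AEs. The documents do not give it; range taken 10% to 80%.
- Constant, proportional cause-specific hazards (assumption), with two bounds that drop it.

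**Formulas.**
- Proportion who stop for AEs (cumulative incidence): s × D.
- Kaplan-Meier with other stops censored: the total cumulative hazard is -ln(1-D) and the AE part is s times that, so 1-KM = 1 - (1-D)^s.
- Upper bound, all AE stops after all other stops: sD / (1 - (1-s)D).
- Lower bound, all AE stops first: sD, so no excess.

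**Results at D = 30%.**

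| AE share s | Cumulative incidence | 1-KM | Excess (points) | Relative excess | Upper bound |
|---|---|---|---|---|---|
| 10% | 3.0% | 3.5% | 0.5 | 17% | 4.1% |
| 20% | 6.0% | 6.9% | 0.9 | 15% | 7.9% |
| 1/3 | 10.0% | 11.2% | 1.2 | 12% | 12.5% |
| 50% | 15.0% | 16.3% | 1.3 | 9% | 17.6% |
| 80% | 24.0% | 24.8% | 0.8 | 3% | 25.5% |

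Worked row: s = 1/3 gives 0.30/3 = 10.0% and 1 - 0.7^(1/3) = 11.2%. A simulation of 200,000 subjects gave 10.1% and 11.3%.

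**Consistency check.** At s = 1/3 the AE curve ends at 11.2% and the non-AE curve at 1 - 0.7^(2/3) = 21.2%. Together they make 32.4%, although only 30% stopped.

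**Smaller total loss.** At D = 10% and s = 1/3 the values are 3.3% and 3.4%.

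**Arms.** For the same pattern of AE stops, the excess differs between arms only if non-AE stopping differs. Illustration (assumed rates): AE stops 10% in each arm, non-AE stops 10% in one and 20% in the other. 1-KM is 1 - 0.8^(1/2) = 10.56% against 1 - 0.7^(1/3) = 11.21%, an apparent difference of 0.65 points where there is none.

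**The case against.** **The right quantity is already reported.** SAP 4.5.2 keeps the cumulative incidence plot and tabulates TEAEs leading to discontinuation. SAP 6.1 itself asks for counts and percentages by primary reason and arm. This stands, and it limits the harm to an inconsistent extra figure. It does not make that figure right.

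**The change is too small to list.** SAP 1 says that 4.8 covers major deviations. But 4.8 also records the renaming of the explorative endpoints, so the threshold in practice is low.

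**Censoring is not stated.** True. It is an inference from applying Kaplan-Meier to one cause, though the usual one.

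**The two plots may not cover identical data.** SAP 6.1 speaks of AEs and names no analysis set; 4.5.2 speaks of TEAEs, in the safety set. The endpoint is therefore essentially, not exactly, the same. The site 613 stops matter only if the 6.1 plot includes those subjects.

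**The size rests on assumptions.** This also stands. The 30% is an allowance, not an observed rate. Protocol Table 14 shows 72 of 76 and 244 of 249 subjects in cohorts 1 and 2 reaching period 4, a loss of 9/325 = 2.8%. At that level, with s = 1/3, the two methods give 0.93% and 0.94%; later losses are not given. Protocol 1.2 says the common local reactions typically arose in the first 1-2 days after initial intake. If AE stops are similarly early, the excess shrinks towards zero.

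**Stronger readings that the documents do not support.**
- A reader might add the exacerbation stopping rule ("If the subject experiences 2 severe asthma exacerbations within a 12 consecutive months period") to the competing events. Exacerbations are recorded on the AE form (Protocol 15.8, SAP 7.1.1.1), and Protocol 5.2 makes an involved AE the primary reason for leaving the trial. Such stops may well count as AE stops.
- A reader might conclude that the arm comparison is distorted. No discontinuation rates by arm are given, so this is possible but not shown.
- A reader might put a total above 30% into the formula. The documents offer no basis for one.

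**Conclusion.** The point holds as a conflict of text and method, with a modest effect. SAP 6.1 departs from Protocol 15.4 and SAP 4.5.2 without recording the change, and Kaplan-Meier is the wrong estimator for a single cause of discontinuation when other causes compete.

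The direction is certain once other stops are censored: 1-KM is never below the cumulative incidence, and it exceeds it whenever some non-AE stops precede some AE stops. The size is not certain. It is about 0.5 to 1.3 percentage points under the stated assumptions, at most 1.1 to 2.6 points over the same AE shares if all AE stops came last, and nil if they all came first.

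No hypothesis test, multiplicity step or sample size depends on the plot. What is at stake is the consistency and correct reading of a named tolerability endpoint.

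**What to change.** In SAP 6.1, restrict Kaplan-Meier to overall treatment discontinuation. For discontinuation due to AEs, refer to the SAP 4.5.2 plot and state there that it is the cumulative incidence function (Aalen-Johansen), shown by treatment arm, with all other reasons for stopping treatment as competing events. Name the analysis set, and say whether stops triggered by asthma exacerbations count as AE stops.

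If the sponsor prefers to keep the Kaplan-Meier version, list it in SAP 4.8, state the censoring rule, and label the curve so that it is not read as the proportion who stopped for AEs.

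The cost is a sentence or two of text. The cumulative incidence plot is already planned, so no new data or analysis is needed. If the SAP can no longer be amended, the change can be documented in the trial report, as Protocol 15 provides for departures from the final SAP.

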# 6.2 Baseline characteristics

Demographic variables (including age, sex, race, ethnic origin, country/region, weight, height, and body mass index [BMI]) will be summarised by treatment group.

Baseline characteristics (e.g. baseline asthma status, inhaled corticosteroid use, duration of HDM AR/C and asthma, and HDM wheal size from SPT, allergen sensitivity (HDM only, HDM + others)) will be summarised by treatment group.

# 6.3 Medical history

Medical history will be summarised by treatment group.

# 6.4 Prior and concomitant therapy

Prior and concomitant medication will be summarised separately by treatment group.

Concomitant medication and illness will be summarised by means of descriptive statistics.

Type of document Document ID	Date: Version: Status:	11-Aug-2022 4.0 Final	
INTERNAL USE	Page:	45 of 79	

# 7 SUPPORTING DOCUMENTATION

# 7.1 Appendix 1: Definitions and derivations

#### 7.1.1 Derivation of endpoints from eCRF data

#### 7.1.1.1 Clinically relevant and severe asthma exacerbation endpoints

The source for deriving the clinically relevant asthma exacerbation and the severe asthma exacerbation endpoints is the AE form of the eCRF. On the AE form the clinically relevant asthma exacerbations are reported with an AE number, a start and a stop time/date and the criterion/criteria fulfilled for the event being categorised as a clinically relevant or severe asthma exacerbation. If at least 1 of the 4 criteria listed in section **1.1.5** is fulfilled, the event is considered a clinically relevant asthma exacerbation. If at least 1 of the 4 criteria listed in section **1.1.5** is fulfilled, the event is considered a clinically relevant asthma exacerbation. If at least 1 of last 3 criteria listed in section **1.1.5** is fulfilled, the event is additionally considered to be a severe asthma exacerbation.

A clinically relevant asthma exacerbation must be separated by more than 7 days from a previous clinically relevant asthma exacerbation in order to be considered an individual event, i.e. the difference between the start date of an event (i) and the stop date for the previous event/events (i-1) must be more than 7 days:

#### AE Start $data_{event=i} - AE$ Stop $date_{event=i-1} > 7$ days

If there are 7 days or less between 2 or more successive clinically relevant asthma exacerbations, the asthma exacerbations will be considered 1 single event starting with the start date of the first asthma exacerbation and ending with the stop date of the last asthma exacerbation. If either clinically relevant asthma exacerbation fulfils 1 of the criteria for being a severe asthma exacerbation the entire event is considered to fulfil that criterion.

#### 7.1.1.2 Annualised rate of clinically relevant asthma exacerbations in period 4

The efficacy assessment period (period 4) begins on the 1st of September for all subjects and lasts until the end of trial visit or discontinuation from IMP. The annualised rate of clinically relevant asthma exacerbations is calculated for each subject as the number of observed clinically relevant asthma exacerbations divided by the time in years in period 4. For the statistical analyses of clinically relevant asthma exacerbations based on a negative binomial regression model the number of clinically relevant asthma exacerbations will be the response variable and the log10 transformed time in years in period 4 will be the corresponding offset.

For each subject, the number of clinically relevant asthma exacerbations is the sum of all clinically relevant asthma exacerbations with a start date in period 4 while the subject is still on IMP. The time in period 4 is calculated as the time in years from start in period 4 until last day of IMP intake, i.e.:

# $Time_{Years} = Years(date_{Last IMP} - date_{Start period 4} + 1).$

A subject who discontinues IMP prior to period 4 will not have any observations of the clinically relevant asthma exacerbations in period 4 and is therefore not included in the primary efficacy analysis.

For a subject who discontinues IMP prematurely in period 4, all available data in period 4 until IMP discontinuation will be used. The number of clinically relevant asthma exacerbations is the sum of all clinically relevant asthma exacerbations with a start date in period 4 before IMP discontinuation.

Type of document	Date:	11-Aug-2022	
Document ID	Version:	4.0	
	Status:	Final	
INTERNAL USE	Page:	46 of 79	

The time with observations in period 4 is the time in years from start of period 4 until the last day of IMP intake, if this date is a partial date, it is imputed. If the last day of IMP intake is unknown, the date of last contact is used instead.

Example 1: A subject is lost to follow up in period 4 and the date of last dose of IMP is unknown. The last point of contact for collecting asthma exacerbations data was telephone contact 4 (TC 4). The subject reported 1 clinically relevant asthma exacerbation with an event start date in period 4, and the time from start of period 4 until TC4 is 93 days. This subject will contribute with 1 asthma exacerbation and a duration time of 93/365=0.25 years in period 4. The annualised rate for this subject is 4 events per year.

Example 2: A subject discontinues IMP due to AEs but continues in the trial. The date of last IMP intake corresponds to 250 days of treatment in period 4 and the subject did not experience any clinically relevant asthma exacerbations that started in period 4 while the subject was still on IMP. This subject will contribute with 0 asthma exacerbations and a duration time of 250/365=0.68 years in period 4. The annualised rate for this subject is 0 events per year.

#### 7.1.1.3 Annualised rate of severe asthma exacerbations in period 4

The annualised rate of severe asthma exacerbations in period 4 is calculated in the same way as the annualised rate of clinically relevant asthma exacerbations in period 4 as described in section **7.1.1.2**. IMP discontinuation is handled in the same way as described in section **7.1.1.2**.

#### 7.1.1.5 ACQ/ACQ-IA

Subjects aged at least 11 years will self-complete the asthma control questionnaire (ACQ) when possible. Otherwise, an interviewer administered version (ACQ-IA) will be used. For subjects aged 5-10 years (both inclusive) the ACQ-IA will be used. ACQ/ACQ-IA will be completed by all subjects during the trial at V3, V5, V6, V7, V8, V9, V10 and V11.

The questionnaire contains a total of 7 items: 5 questions are related to asthma symptoms, 1 question is related to SABA medication use and 1 item is related to FEV1, the latter being calculated based on the FEV1 measurement. Subjects are asked to recall their experiences during the previous 7 days and respond to each question using a 7-point scale which is translated into a scale ranging from 0 to 6. The items are equally weighted and the ACQ/ACQ-IA score is the average of the 7 items and therefore between 0 (well controlled) and 6 (extremely poorly controlled).

Type of document Document ID INTERNAL USE	Date: Version: Status: Page:	11-Aug-2022 4.0 Final 47 of 79	ALK

#### 7.1.1.8 Global evaluation of rhinitis and asthma

At the final visit the subjects will be asked about their perception of the treatment efficacy during the treatment period answering the following question regarding rhinitis: "Compared to your rhinitis symptoms before starting treatment with the IMP, how are you feeling overall now?".

Subjects will additionally be asked about their perception of the treatment efficacy during the treatment period answering the following question regarding asthma: "Compared to your asthma symptoms before starting treatment with the IMP, how are you feeling overall now?".

A subject answering "better" or "much better" will be categorised as "improved". A subject answering "much worse", "worse" or "the same" will be categorised as "not-improved".

Type of document	Date:	11-Aug-2022	
Document ID	Version:	4.0	
	Status:	Final	
INTERNAL USE	Page:	48 of 79	

